5.2 PARTICIPANT EXCLUSION CRITERIA

- 1) Patients hospitalized within the last 30 days ONLY if the institution mandates these patients are observed. Otherwise, these patients remain eligible.
- 2) Transplanted organ of any kind or ventricular assist device patient;
- 3) End stage renal disease, on dialysis, or eGFR < 20 mL/min;
- 4) Acute coronary syndrome (e.g. EKG changes consistent with ischemia or troponin elevation secondary to ACS as per the treating ED clinician);
- 5) Other acute co-morbid conditions (e.g. sepsis, altered mental status);

6) Patients who require ventilatory support of any kind or intravenous vasodilators/vasopressor/inotropic support at the time of ED disposition

7) Pregnant patients or any patient who has been pregnant in the last 3 months

8) ≤ 18 years of age

9) Any patient who in the opinion of the clinician or investigator should not be in an obs unit or requires ICU level care or will require inpatient rehabilitation or skilled nursing facility after discharge from the ED or hospital

10) Planned discharge from the emergency department

11) De novo (new onset) AHF

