5 STUDY ENROLLMENT AND WITHDRAWAL

5.1 PARTICIPANT INCLUSION CRITERIA

- 1) ED physician clinical diagnosis of AHF;
- 2) Planned admission for AHF
- 3) Systolic blood pressure > 100mmHg*, heart rate < 115bpm. The last HR and SBP should be within 1 hour of randomization.
- 4) Previous history of HF

*Patients with atrial fibrillation but controlled HR are eligible

For Caregiver Burden assessments. The eligibility criteria for a caregiver: 1) person either self-identifies, or when asked identifies themselves, as the primary caregiver for the patient. If there are multiple caregivers, the person who self-identifies as providing the most care will be asked to provide verbal informed consent. This part of the investigation poses no more than minimal risk to the subject and caregivers will be provided with information about the study and the processes for the initial and 30 day follow up questionnaires. For patients with no caregiver identified, no caregiver assessment will be performed.

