5.3 STRATEGIES FOR RECRUITMENT AND RETENTION

Sites will be initiated only after IRB approval and site training. Each site has well-established procedures for identifying potential subjects for AHF clinical trials. Broadly, these are based on electronic screening of 'tracking boards' in the ED, alert systems generated by the electronic health record, and direct interaction with ED caregivers. Each site will also be required to utilize a '*boots-on-the-ground*' approach. *While electronic aids may be used, each site must have research staff physically walk through the ED frequently throughout the day or stationed in the ED.* Patients with AHF will be pre-screened by dedicated, trained, experienced research personnel to determine if eligibility criteria are met. Patients will then be approached to ascertain their willingness to participate after discussion with the patient's primary caregiving team. Only after written informed consent will randomization occur.

As a comparative effectiveness trial, the inclusion/exclusion criteria are relatively broad compared to other therapeutic clinical trials.

Screen Failures:

Patients who sign an informed consent but who are not randomized, or after randomization have a change in clinical status making them ineligible, will be considered Screen Failures. Only data for randomized patients will be entered into the CRF. Serious adverse events should be reported for these patients from the time the ICF is signed through the time

that the patient is declared a screen failure. One expected reason for screen failure will be a change in plan to discharge the patient from the ED.

Minimizing loss to follow-up (LTFU), as well as completion of 30-day and 90-day vital status assessments and QoL/Caregiver Burden questionnaires, are critical to study success. Every effort will be made to ensure follow-up with patients and caregivers at 30 and 90 days, including phone call, text messaging, email, regular mail, and electronic health record review. Based on the extensive experience at each site, we do not anticipate a large LTFU rate. However, our sample size calculations account for attrition (see below).

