7.3 STUDY SCHEDULE

7.3.1 SCREENING

A signed and dated informed consent form will be obtained before any study-specific screening procedures are performed. Results of evaluations obtained as part of routine medical care, which are performed prior to obtaining

informed consent, may be used in place of the protocol-specified evaluations. Patients will acknowledge and agree to the use of this information for the study by giving informed consent.

At the Baseline Visit, patients will be assigned by the IWRS a unique permanent identification number (referred to as the patient identification number) such that all randomized patients from each center are given consecutive identification numbers by the IWRS in successive order of inclusion. We will utilize the REDCap randomization module.

Prospective study patients will have presented to the hospital for urgent therapy for AHF. Potential patients will be identified either en route to or upon arriving at the ED/hospital. Routine assessments associated with usual patient care may be used for the purposes of screening and may be completed in any order. Study specific procedures must be completed only after Informed Consent is obtained.

Randomization will occur during the patients ED stay. This may occur at any time during their ED stay.

The following procedures will be performed prior to or during Screening:

- Obtain written informed consent (must be performed as the first study-specific procedure)
- Review and record medical history
- Record prior and concomitant medications
- Physical examination (including height and weight when reasonably possible)
- Vital signs measurements (includes systolic and diastolic blood pressures, heart rate, body temperature, oxygen saturation reading and respiratory rate)
- 12-Lead Electrocardiogram per standard practice
- Blood collection for local laboratory tests, including BNP or NT-proBNP, and pregnancy test if applicable per local standard practice.
- Inquiry about Adverse events

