7.3.2 ENROLLMENT/BASELINE

Patients who continue to fulfill all of the inclusion/exclusion criteria will be randomized. Randomization will occur via central IWRS system.

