10.1.1 ENDPOINTS AND RATIONALE

To ensure patient-centered endpoints, we twice met with patients and caregivers through two community engagement studios.⁵⁴ Patients prefer to be healthy and have a good QoL. If a safe alternative is available, patients prefer not to be hospitalized.

The **primary outcome** is **days alive and out of hospital (DAOOH) at 30 days post-randomization**. Unlike time-to-event analyses that ignores repeat events and gives equal weight to components of a composite endpoint,⁵⁵ DAOOH accounts for both frequency and duration of hospitalization and also weights mortality most heavily.^{55,56} This endpoint has also been suggested as a quality metric rather than re-hospitalization alone.⁵⁷

The **two secondary outcomes** are 1) **QoL using the KCCQ**. Patients desire not only to live longer, but to live better; or at minimum, not be worse after an acute health care related event.⁵⁸ Patients with advanced HF would trade survival time (or days alive) for a better QoL.⁵⁸ Our pilot work supports the feasibility of assessing QoL in the acute setting and suggests changes in scores are related to hospital re-visits.⁵⁹ We hypothesize that fewer days in the hospital in our SSU arm will also lead to a greater QoL. Interviews of hospitalized AHF patients suggest **they would prefer a shorter hospital stay or avoid an admission altogether**, assuming safety and outcomes are similar or better than hospitalization. Thus, assessing QoL is a key aim.

The KCCQ is a patient-reported, validated survey instrument designed to measure QoL in chronic HF patients.⁶⁰ Lower scores equal lower patient-reported QoL. **KCCQ scores predict adverse outcomes – namely hospitalization and mortality.** Importantly, the KCCQ demonstrates responsiveness to clinical change.⁶⁰⁻⁶²

A change of five points has been previously shown to be clinically significant, and will be assessed prior to discharge and day 30 post-randomization.⁶²

2) Cost effectiveness analysis, described in detail below.

NOTE: For patients randomized to SSU who worsen PRIOR to going to SSU, this will be counted the same as a hospitalization from the SSU.

ADDITIONAL ENDPOINTS

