10.6 MEASURES TO MINIMIZE BIAS

10.6.1 ENROLLMENT/ RANDOMIZATION/ MASKING PROCEDURES

Patients will be randomized 1:1 to one of the two study arms, but stratified by site to ensure equal site representation. A central computer generated randomization scheme with random block sizes of two, four, and six will be created, stratified by site. The REDCap randomization module will be utilized to generate the randomization schema and patient allocation.

Due the nature of the intervention and the clinical setting, this is an unblinded trial.

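### The protocol does not ensure that exclusion 6 is settled before open allocation, and its Screen Failure rule allows a patient who then becomes ineligible to be removed with the arm known

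*Combined protocol and SAP*

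**What the plan says.** Exclusion 6 in Section 5.2 removes "Patients who require ventilatory support of any kind or intravenous vasodilators/vasopressor/inotropic support at the time of ED disposition". The protocol does not say whether ED disposition is the decision on where the patient goes or the moment of leaving the ED.

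On timing, Section 7.3.1 states: "Randomization will occur during the patients ED stay. This may occur at any time during their ED stay". Heart rate and blood pressure do have a randomization anchor in Section 5.1: "The last HR and SBP should be within 1 hour of randomization". Exclusion 6 has none. Section 10.6.1 states: "Due the nature of the intervention and the clinical setting, this is an unblinded trial".

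Two passages suggest that eligibility should be complete at allocation. Inclusion 2 in Section 5.1 requires "Planned admission for AHF", and Section 7.3.2 says "Patients who continue to fulfill all of the inclusion/exclusion criteria will be randomized".

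Three passages bear on a patient whose status changes afterwards:

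- Section 5.3: patients who "after randomization have a change in clinical status making them ineligible, will be considered Screen Failures". It asks for serious adverse events in these patients only up to that declaration.
- Sections 5.4.2 and 10.3: the full analysis set (FAS) is all randomized patients, less those randomized in error who received no study intervention.
- Section 10.1.1: "For patients randomized to SSU who worsen PRIOR to going to SSU, this will be counted the same as a hospitalization from the SSU". There is no matching rule for usual care.

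**The concern.** In an open trial, eligibility should be fixed on information recorded before allocation. If a criterion can be judged or revisited later, staff who know the assigned destination also decide who counts as eligible. Here the criterion concerns ventilatory or intravenous vasoactive support. Patients who newly need it would plausibly have fewer days alive and out of hospital (DAOOH) than the others.

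The Screen Failure rule turns this timing gap into a possible bias. It gives a written ground for declaring a randomized patient ineligible after the arm is known. If that happens more readily in one arm, the groups compared are no longer the groups randomized.

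**Working it through.** **1. When is exclusion 6 judged?** Two readings of ED disposition are open.

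- Disposition is the decision to admit. Inclusion 2 and Section 7.3.2 would then usually place the assessment before randomization.
- Disposition is departure from the ED. A patient randomized early in the stay would then be assessed later, with the arm known.

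No section chooses between them, and Section 7.3.1 does not require a disposition decision before randomization. Section 5.3 expects some plans to change to ED discharge, so a plan to admit is not treated as final.

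**2. What happens to a patient who is eligible at randomization and then worsens in the ED?**

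| Rule | SSU arm | Usual care |
|---|---|---|
| Section 5.3, Screen Failure | may be declared a Screen Failure | may be declared a Screen Failure |
| Section 10.1.1, note | kept, counted as a hospitalization from the SSU | silent |
| Sections 5.4.2 and 10.3, FAS | kept | kept |

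No order of precedence is given. Section 5.3 does not say in terms that a Screen Failure leaves the analysis, but the label and the early end of safety reporting point that way. If Section 10.1.1 governs the SSU arm and Section 5.3 governs usual care, only usual-care patients are removed, which would work against the SSU arm. If Section 5.3 is applied to SSU patients, the bias runs the other way.

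**3. The plan's sample size (Section 10.5) reproduces.** Inputs: difference 1 day, SD 3.9, two-sided alpha 0.05, power 80%, one interim look at half the data, attrition 10%.

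- Fixed sample: 2 × [3.9 × (1.960 + 0.842)]² = 238.8, so 239 per arm.
- With O'Brien-Fleming spending (inflation 1.0037): 239.7, so 240 per arm.
- With attrition: 480 / 0.90 = 533.3, so 534.

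The point does not rest on an arithmetic error.

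**4. Illustration of selective removal.** The documents give no rate, so both inputs are assumptions: *f*, the share of one arm removed, and *d*, how many fewer DAOOH those patients average than those kept.

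- Bias = *f* × *d*.
- SE = 3.9 × √(1/240 + 1/[240(1 − *f*)]).
- Two-sided type I error = Φ(−1.96 + bias/SE) + Φ(−1.96 − bias/SE), for a fixed-sample z test.

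For *f* = 5% and *d* = 5: bias = 0.25 day; SE = 3.9 × √(1/240 + 1/228) = 0.361; bias/SE = 0.69; type I error = 10.7%.

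| Share removed from one arm | *d* = 3 days | *d* = 5 days | *d* = 10 days |
|---|---|---|---|
| 2% | 0.06 day; 5.3% | 0.10 day; 5.9% | 0.20 day; 8.6% |
| 5% | 0.15 day; 7.0% | 0.25 day; 10.7% | 0.50 day; 28.4% |
| 10% | 0.30 day; 13.0% | 0.50 day; 27.7% | 1.00 day; 78.1% |

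Each cell gives the bias and then the type I error.

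**5. Even loss from both arms.** If 2%, 5% or 10% were lost equally on top of the planned attrition, power would be about 79.4%, 78.2% or 76.0%. Selective removal matters more than lost numbers.

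**The case against.** The best defence is that disposition means the decision to admit. Inclusion 2, exclusion 10 (planned ED discharge) and Section 7.3.2 all assume that a disposition plan exists when eligibility is checked, and Section 10.4.2 uses a separate term for the time a patient leaves the ED. This stands as a plausible reading. A reader might infer that exclusion 6 cannot be known at randomization, or that Section 7.3.2 cannot be met. The documents do not support that. They show only that prior assessment is not ensured.

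A second defence is that a patient who was eligible when randomized was not randomized in error, so the FAS keeps that patient, and Section 5.4.1 asks for follow-up of all randomized patients. This is right as far as those sections go, but neither is ranked above Section 5.3. It is also fair to say that the Screen Failure clause reaches every criterion that depends on clinical status. Exclusion 6 is where the undefined time point exposes it most directly.

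A reader might also infer that SSU patients diverted before reaching the unit dilute the effect beyond what was planned. The documents do not support a figure for this. Section 10.5 says the power calculation already allows for 40% admission from the SSU (0.40 × 267, about 107 patients), and Section 10.1.1 counts early worsening in that category. Nor can the same patient be both removed, which gives selection bias, and retained, which gives dilution.

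**Conclusion.** The concern holds in this form. The protocol does not ensure that exclusion 6 is settled before open allocation, and its rules on patients who become ineligible afterwards conflict with one another and differ by arm. The harm is possible selective removal after randomization.

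Its size is unknown. The tabulated figures assume removal from one arm only and assumed values of *f* and *d*. They show how the bias would scale and do not predict it for this trial. At 2% removed and a 3-day difference the effect is negligible. At 5% and 5 days it is a quarter of the target difference. If the sponsor confirms that the decision to admit always precedes randomization, and that the FAS definition overrides Section 5.3, most of the problem becomes one of wording. The present text says neither.

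**What to change.** - Define ED disposition. Require the disposition decision and the exclusion 6 assessment to be recorded before the REDCap randomization opens, and change Section 7.3.1 to match.
- Leave the clinical content of exclusion 6, and any change in who is eligible, to the sponsor, who should reconcile Sections 5.1, 5.2 and 7.3.1. Simply moving the criterion's time point to randomization would not be neutral: a patient on support at randomization but off it at disposition would move from eligible to excluded.
- Delete the post-randomization clause from the Screen Failure definition in Section 5.3, so that the term covers only consented patients who were not randomized. Changing the time point alone would leave this route open.
- State that any patient in either arm who was eligible at randomization and later worsens is followed and analysed as randomized. Align Sections 5.3, 5.4.2, 10.1.1 and 10.3 with that statement.

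The cost is a few edits and required fields on the randomization form. Randomization would come somewhat later in the ED stay, and a few patients who move quickly may be missed. The sample size does not need to change.

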5.3 STRATEGIES FOR RECRUITMENT AND RETENTION

Sites will be initiated only after IRB approval and site training. Each site has well-established procedures for identifying potential subjects for AHF clinical trials. Broadly, these are based on electronic screening of 'tracking boards' in the ED, alert systems generated by the electronic health record, and direct interaction with ED caregivers. Each site will also be required to utilize a '*boots-on-the-ground*' approach. *While electronic aids may be used, each site must have research staff physically walk through the ED frequently throughout the day or stationed in the ED.* Patients with AHF will be pre-screened by dedicated, trained, experienced research personnel to determine if eligibility criteria are met. Patients will then be approached to ascertain their willingness to participate after discussion with the patient's primary caregiving team. Only after written informed consent will randomization occur.

As a comparative effectiveness trial, the inclusion/exclusion criteria are relatively broad compared to other therapeutic clinical trials.

Screen Failures:

Patients who sign an informed consent but who are not randomized, or after randomization have a change in clinical status making them ineligible, will be considered Screen Failures. Only data for randomized patients will be entered into the CRF. Serious adverse events should be reported for these patients from the time the ICF is signed through the time

that the patient is declared a screen failure. One expected reason for screen failure will be a change in plan to discharge the patient from the ED.

Minimizing loss to follow-up (LTFU), as well as completion of 30-day and 90-day vital status assessments and QoL/Caregiver Burden questionnaires, are critical to study success. Every effort will be made to ensure follow-up with patients and caregivers at 30 and 90 days, including phone call, text messaging, email, regular mail, and electronic health record review. Based on the extensive experience at each site, we do not anticipate a large LTFU rate. However, our sample size calculations account for attrition (see below).

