8.1 SPECIFICATION OF SAFETY PARAMETERS

Mortality, re-hospitalization, and ED visits through 30 and 90 days will be assessed for safety as well as efficacy

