8.1.2 DEFINITION OF SERIOUS ADVERSE EVENTS (SAE)

An AE will be classified as an SAE if:

- It results in death (i.e., the AE actually causes or leads to death).
- It is life threatening (i.e., the AE, in the view of the investigator, places the subject at immediate risk of death. It does not include an AE that, had it occurred in a more severe form, might have caused death).
- It requires or prolongs inpatient hospitalization. Admission from the SSU itself does not count as an SAE, but an expected outcome. However, if in the investigators judgment, admission from the SSU was due to some other complication of the study protocol, rather than an expected outcome, it should be reported as an SAE

SPECIFIC REPORTABLE SAE for SSU/OU arm patients:

- Cardiac arrest

- Need for intubation or positive pressure ventilation
- It results in persistent or significant disability/incapacity (i.e., the AE results in substantial disruption of the subject's ability to conduct normal life functions).
- It is considered a significant medical event by the investigator based on medical judgment (e.g., may jeopardize the subject or may require medical/surgical intervention to prevent one of the outcomes listed above).

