8.4 REPORTING PROCEDURES

8.4.1 ADVERSE EVENT REPORTING

The study period during which AEs must be reported begins after informed consent is obtained and initiation of study treatment and for 5 days after randomization. Patients will be followed out to 90 days for death, ED utilization, and re-hospitalization as part of the study outcomes, which will also count as safety measures. Subject's hospital discharge summaries will be examined at hospital discharge and all non-exempt AEs will be investigated by examining necessary medical records.

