8.4.2 SERIOUS ADVERSE EVENT REPORTING

All SAE's will be reviewed within 48 hours and all AE's within 7 days of discovery. SAE's will be followed through the entire follow up period (i.e. through day 30). Any SAE discovery will be reported to the DCC who will then report to the DSMB. If placebo treated patient, standard reporting to the IRB will occur. If active treated patient, and deemed to be related to drug, the SAE will be reported to the DSMB chair within 7 business days by email, fax, or phone of any fatal or life-threatening adverse event that is unexpected.

15 Calendar Day Written Report

The Investigator will also be required to notify the IRBs and all participating investigators, in a written Safety Report, of any serious, unexpected AE that is considered reasonably or possibly related to the strategy-of-care arm

72 hour reporting

For the discovery of an unexpected serious adverse event thought to be related to study procedures the Investigator(s) will notify the Chair of the DSMB by email within 72 hours.

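### Section 5.3 lets a randomized patient be declared a screen failure and ends SAE reporting at that point, in conflict with the 5-day safety window and the follow-up rules for randomized patients

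*Combined protocol and SAP*

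**What the plan says.** The Screen Failures paragraph of Section 5.3 covers two groups under one label. The first has consented but is never randomized. The second is made up of patients who "or after randomization have a change in clinical status making them ineligible, will be considered Screen Failures". The paragraph then sets one safety rule: "Serious adverse events should be reported for these patients from the time the ICF is signed through the time" of the screen-failure declaration. It makes no exception for the randomized group and does not say when the declaration is made. It also states that "Only data for randomized patients will be entered into the CRF", and gives a changed plan, to discharge from the ED, as an expected reason for screen failure, without saying whether that comes before or after randomization.

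Elsewhere the rules for randomized patients are longer:

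- Section 8.4.1 has AE reporting begin after consent "and initiation of study treatment and for 5 days after randomization".
- Section 8.1.1 gives a 5-day AE reporting period for everything except mortality, re-hospitalization and ED visits. The schedule in Section 7.3.7 has AE/SAE assessment through 5 days in both arms.
- Section 8.3 requires AEs of randomized patients to be recorded on the CRF.
- Section 8.4.2 says "SAE's will be followed through the entire follow up period (i.e. through day 30").
- Section 5.4.1 asks that every randomized patient be followed for the whole period, as far as the patient allows.
- Sections 5.4.2 and 10.3 put all randomized patients in the FAS, less only those randomized in error who had no study intervention.
- The NOTE in Section 10.1.1 counts a patient assigned to the SSU who worsens before arriving there as admitted from the SSU.

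**The concern.** A screen failure is ordinarily someone who never entered the trial. Applied after randomization, the label closes safety reporting for a patient who has been allocated, and does so because that patient's clinical state has changed. A site cannot both stop at the declaration, as Section 5.3 says, and carry on for 5 days, as Sections 7.3.7, 8.1.1 and 8.4.1 say.

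What is directly at stake is the completeness of SAE data in the days after a change of status. A secondary matter is the label itself. Section 10.6.1 makes this an unblinded trial, so staff know the arm when they decide whether a patient is still eligible. If a site took the label to mean that the patient had left the study, outcomes might go uncollected, possibly not equally in the two arms.

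**Working it through.** The plan gives no figure for post-randomization screen failures, so the check is a comparison of text.

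**1. Can the group exist?** Yes. Section 7.3.1 allows randomization at any point in the ED stay. One exclusion in Section 5.2 is judged later: "Patients who require ventilatory support of any kind or intravenous vasodilators/vasopressor/inotropic support at the time of ED disposition". A patient can be eligible when randomized and meet that exclusion at disposition.

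**2. Do the triggers overlap with safety events?** Partly. Ventilatory support is an exclusion under Section 5.2, and "Need for intubation or positive pressure ventilation" is on the list of specifically reportable SAEs for the SSU arm in Section 8.1.2. The triggering event comes before the declaration, so it remains reportable under Section 5.3. What falls outside is anything that follows.

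**3. The two reporting windows.** Section 8.1.2 defines an SAE as a class of AE, so the 5-day AE window covers SAEs, and Section 7.3.7 names them. Let d be the time in days from randomization to the declaration.

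| Rule | Reporting of SAEs ends |
|---|---|
| Section 5.3 | at d |
| Sections 7.3.7, 8.1.1, 8.4.1 | at 5 days (from randomization in Section 8.4.1) |

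The gap is 5 − d days when d is below 5. A declaration in the ED on the day of randomization (d near 0) leaves a gap of nearly 5 days; a declaration one day after randomization leaves 5 − 1 = 4 days.

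**4. What is still collected in the gap?** Section 8.1 says "Mortality, re-hospitalization, and ED visits through 30 and 90 days will be assessed for safety as well as efficacy", and Section 8.4.1 repeats the 90-day follow-up of these outcomes. Section 5.3 does not end that follow-up. The stated loss is therefore SAEs other than these three outcomes, between the declaration and day 5. A cardiac arrest that the patient survives on day 2, after a declaration on day 0, is an example.

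**5. Analysis set.** Section 5.3 does not mention the FAS. Sections 5.4.2 and 10.3 keep every randomized patient unless randomization was an error and no study intervention was received. Becoming ineligible later is not an error of randomization, so the patient stays in. Section 5.3 also has CRF data entered for randomized patients. The Section 10.1.1 NOTE keeps and counts an SSU-arm patient whom Section 5.3 could label a screen failure. It has no counterpart for usual care.

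**6. Sample size.** With 240 per arm and 10% attrition, 2 × 240 / (1 − 0.10) = 533.3, rounded up to the plan's 534. None of these inputs depends on the screen-failure wording.

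**The case against.** The strongest reply is that the conflict is thinner than it looks. Section 8.4.1 opens the AE window after consent and the start of study treatment, so it might never open for someone who becomes ineligible in the ED before assigned care begins. That is a fair reading of that sentence, but the window's end is tied to randomization, and Sections 7.3.7, 8.1.1 and 8.3 carry no treatment-start condition. The conflict remains.

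A reader might infer that SAE reporting is lost as far as day 30, from Section 8.4.2. The documents do not support this. That section says SAEs are followed, which may mean following events already reported. It also carries placebo and drug wording that does not belong to this trial. Sections 7.3.7 and 8.1.1 limit new collection of other events to 5 days.

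Section 8.2.3 exempts many events from regulatory reporting, among them mechanical ventilation and vasopressor support. This narrows the practical loss, though it concerns regulatory reporting and does not cancel the CRF recording required by Section 8.3.

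A reader might also infer that the plan drops these patients from the primary analysis and so biases DAOOH. No passage says so, and Sections 5.4.2 and 10.3 say the reverse. Any shift in the DAOOH contrast would need an assumed removal rate, an assumed mean for those removed and an assumed imbalance between arms, none of which the documents give. This part of the objection stands in full: no size should be attached.

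**Conclusion.** Section 5.3 is wrong as written. It gives sites an instruction on SAE reporting for some randomized patients that cannot be followed together with Sections 7.3.7, 8.1.1, 8.3 and 8.4.1, and it is at odds with the follow-up instruction in Section 5.4.1. The loss it creates is bounded: SAEs other than death, ED visits and re-hospitalization, over at most the 5 days after randomization, in however many patients are so labelled. The documents do not give that number. The bound assumes that outcome follow-up to 90 days continues, as nothing in Section 5.3 stops it.

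The misfit with the FAS and with the Section 10.1.1 NOTE is an inconsistency of labelling and not a stated exclusion. Bias in the primary comparison is a risk only if unblinded sites act on the label as if the patient were out of the study.

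**What to change.** In Section 5.3, delete the limb of the definition that applies after randomization, so that a screen failure is someone who consented and was never randomized. Then state that:

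- every validly randomized patient has the same AE/SAE reporting and the same 30- and 90-day follow-up, in both arms;
- every such patient stays in the FAS in the assigned arm;
- a change of status after randomization, including a later plan to discharge from the ED, does not make a patient misrandomized.

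Reconcile Sections 5.3, 5.4.1, 5.4.2, 7.3.7, 8.1.1, 8.3, 8.4.1, 8.4.2, 10.1.1 (NOTE) and 10.3. In doing so, clarify whether Section 8.4.2 sets a collection window or only follow-up of events already reported. Report post-randomization changes of status by arm.

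The cost is an amendment of wording and a few more patients under AE/SAE reporting. The sample size stays at 534.
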